8. SAMPLE

8.1. TARGET POPULATION(S)

For each target population identified in Section 1.2, please describe the target population(s), and explicitly state whether the population(s) differs from those who will be broadly served by the grant. Describe how the target population will be identified. Explicitly state the unit of analysis (e.g., non-residential father, unmarried couple).

Description of Target Population	How is the population different from those who will be broadly served by the grant?	How will the target population be identified?	Unit of Analysis
Target population is community fathers (ages 18 and older), who have children ages 24 and younger and reside in communities with high rates of poverty.	No difference, all program participants will be study participants.	The sample will be identified and recruited by community partner referrals and program staff.	Community adult fathers

8.2. METHODS TO PROMOTE SUFFICIENT PROGRAM PARTICIPATION

Please describe methods to promote sufficient program participation in the table below.

What methods will you use to ensure sufficient sample is recruited, enrolls, and participates in the program?	FAWIC and their community partners will recruit program participants, and Fresno Fatherhood will provide incentives for program retention and completion. The CQI process will address issues regarding program recruitment and enrollment to ensure targets are met.
Who will be responsible for recruiting the evaluation sample?	The evaluation sample will not differ from the program population, in that all participants will be invited to participate in the evaluation. Enrollment into the evaluation will be conducted by the CQI Data Manager who will conduct the informed consent process and proctor the baseline data collection efforts.
Please describe any incentives to be offered for program participation and/or completion and/or data collection and/or participation in the evaluation.	Evaluation Participation – No incentives will be used for the first two data collection waves at baseline and post-test while participants are beginning or still engaged in services. A \$50 incentive in the form of a Giftogram gift card will be given to participants who complete the 1-year follow-up survey.

9. DATA COLLECTION

9.1. CONSTRUCTS AND MEASURES

Clearly articulate the constructs of interest, measures to evaluate those constructs, and specific data collection instruments. Provide any information on the reliability and validity of the data collection instruments. For standardized instruments, you may provide the citation for the instrument.

Construct	Measure	Instrument	Reliability and Validity (if standardized instrument, you provide a citation for the instrument)
Parenting Attitudes	7 items: frequency of key attitudes (categories, 5-point scale)	nFORM Community-Based Fathers Survey (A3: a-g)	nFORM entrance to exit
Parenting Behavior	1 item: hours spent w/ children in last 30 days (interval); 1 item:	nFORM Community-Based Fathers Survey (A2b,	nFORM entrance to OLLE follow-up

	frequency reach out to children (categories, 5 point scale); 7 items: frequency engage in key behaviors (categories, 5-point scale)	A2c, A5b: b-d, f-i)	
Co-Parenting Behavior	11 items: frequency of agreement with key co-parenting behaviors (interval, 5-point scale)	nFORM Community-Based Fathers Survey (A13: a-k)	nFORM entrance to OLLE follow-up
Financial Behavior	2 items: yes or no questions for having a checking/savings account (categories, yes/no response choices)	nFORM Community-Based Fathers Survey (B3 – B3a)	nFORM entrance to OLLE follow-up
Financial Attitudes	7 items: levels of agreement with key financial attitudes (categories, 5-point scale)	OLLE (Online Local Evaluation) Survey:	OLLE pre to post
Employment Behavior	1 item: yes or no do you have an updated resume to give employers (yes/no response choices)	nFORM Community-Based Fathers Survey (B2)	nFORM entrance to OLLE follow-up
Employment Attitudes	8 items: levels of agreement with key employment attitudes (categories, 5-point scale)	OLLE (Online Local Evaluation) Survey:	OLLE pre to post

* you may add rows by hitting the tab button, or right click and select insert row below

9.2. CONSENT

Describe how and when program applicants will be informed of the study and will have the option of agreeing (i.e., consenting to) or declining to participate in the study.

To secure informed consent, participants will attend an orientation/enrollment session (in person) where the Data Manager will describe the evaluation process, the risks, and benefits of participating in the project. Those people that wish to participate in the evaluation will complete an informed consent process and sign an informed consent document / form. All participants will receive a copy of the consent form with contact information for evaluation staff and how to contact the IRB if needed. Informed consent will take place prior to program enrollment and the collection of evaluation data.

9.3. METHODS OF DATA COLLECTION

If the evaluation will collect multiple waves of data, describe the timing of these waves below. When describing follow-up periods, specify whether the follow-up period will be post-baseline, post-random assignment, or post-program completion.

Wave of Data Collection (e.g., baseline, short-term follow-up, long-term follow-up)	Timing of Data Collection
Baseline	Collected immediately following informed consent and enrollment – during the orientation session or first workshop
Post-Test	Collected after the completion of core curriculum programming -during the last workshop session – approximately 4 weeks after enrollment.
1 year Follow-up (post-baseline)	Collected approximately one year after program enrollment/ baseline. Participants who did not complete the program will still be eligible for a follow-up survey as long as they consented to be in the study and took a baseline survey.

For each measure, describe how data will be collected detailing which data collection measures will be collected by which persons, and at what point in the programming or at what follow-up point.

Measure	Timing of Data Collection (baseline, wave of data collection)	Method of Data Collection	Who Is Responsible for Data Collection?	Impact Evaluations Only: Will Methods or Collection Procedures Differ by Study Group?	Administrative Data Only: Will data access require data sharing agreement?
Online Local Evaluation (OLLE) Baseline Survey	Baseline	Participant self-enters survey using online Qualtrics data collection platform	Case Manager and/or facilitator will proctor data collection and assist participants as necessary	N/A	N/A
nFORM Community Fathers Entrance Survey	Baseline	Participant self-enters survey using online nFORM data collection platform	Case Manager and/or facilitator will proctor data collection and assist participants as necessary	N/A	N/A
OLLE Post-Test Survey	Post-Test (approx. 4 weeks after enrollment)	Participant self-enters survey using online Qualtrics data collection platform	Case Manager and/or facilitator will proctor data collection and assist participants as necessary	N/A	N/A
nFORM Community Fathers Exit Survey	Post-Test (approx. 4 weeks after enrollment)	Participant self-enters survey using online nFORM data collection platform	Case Manager and/or facilitator will proctor data collection and assist participants as necessary	N/A	N/A

OLLE 1 Year Follow-up Survey	1 year after enrollment / baseline	Participant self-enters survey using online data collection platform and link – or – Phone interview data collection with evaluation staff	MER survey tracking team member	N/A	N/A
------------------------------	------------------------------------	--	---------------------------------	-----	-----

* you may add rows by hitting the tab button, or right click and select insert row below

9.4. ENSURING AND MONITORING DATA COLLECTION

Describe plans for training data collectors and for updating or retraining data collectors about procedures. Detail plans to regularly review data that have been submitted and to assess and swiftly address problems.

This evaluation will utilize both post-program surveys (completed at the completion of core programming) and follow-up surveys collected one year after enrollment / baseline. The methods for these data collections differ. The primary driver for post-program survey completion is high rates of program retention. This data point will be collected during the last workshop session – after (but during the same session of) the completion of the nFORM post-program data collection. As such only those individuals who complete the program and who are at the data collection session will participate in the post-program data collection. All program participants, even those who do not complete the program, will be sent a 1-year follow-up survey if they consent to be part of the evaluation and have taken a baseline survey.

All program staff and evaluation staff will undergo a rigorous set of trainings to prepare for the evaluation. All staff receive an overview and introductory training to present the goals and objectives of the evaluation effort and its importance to the overall project. Next, all staff receive training on human subject's protection and are required to pass a certification test on the subject matter. All staff will also receive a detailed training on the details of the evaluation including the evaluation tools, timing, and data collection process and the role and importance of data accuracy.

In addition, the data manager and the primary local evaluation staff will undergo a rigorous training process to better understand the context of HMRF research, training on data collection procedures they will be responsible for, and training on the nFORM system and use of nFORM data in a CQI process. MER is creating networks of CQI data managers and Evaluation Project Managers across the 12 projects that we are evaluating so that all staff have access to experienced data managers and evaluation staff who have done this work previously. This training takes the form of weekly training sessions that are currently under way.

Members of the CQI Team will also receive specific training on the MER CQI process that has been developed prior to the launch of data collection or program services. As described elsewhere MER is assisting the program staff in implementing a robust CQI process that will focus on retention as one of the primary areas of program improvement and as such we are anticipating relatively modest levels of attrition for this data collection.

On a bi-weekly basis the data manager, the local evaluation staff and MER technical specialists will be responsible for downloading data from the nFORM and MER On-Line Local Evaluation (OLLE) systems for processing and presentation to the CQI Team for tracking and monitoring performance measurement outcomes (recruitment, enrollment, dosage, completion, referrals, etc.) so that near real time adjustments can be made to program implementation to ensure compliance with program goals and objectives.

All MER training is currently being recorded and as new staff come on board with projects, project staff turnover, or there is a need for refresher training, recorded training material can be shared and accessed with follow-up one-on-one training with the primary Lead Evaluator.

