### Identify study sample

The study sample includes participants who: 1) gave recorded informed consent to be part of the study, and 2) took both an entrance and exit survey (for attitudinal outcomes) or entrance and follow-up survey (for behavioral outcomes). The CONSORT diagram in Appendix C shows exclusion criteria and the anticipated size of the overall study sample. The analytic sample for particular outcome measures will vary based on missing data.

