#### **Analytic approach**

The main goal of this descriptive study is to assess pre-to-post change scores in the attitudinal outcomes listed above, and assess pre-to-one-year follow-up change scores in the behavioral outcomes listed above among program participants before and after primary workshops. We will use paired sample t-tests to assess the magnitude and significance of changes among program participants in the analytic sample for each outcome. For binary economic stability outcomes, we will descriptively report the percent of participants who opened a checking or savings account 1 year after enrollment, compared to the percent who had opened these accounts before the program. For binary employment outcomes, we will descriptively report the percent of participants who did not have a resume 1 year after enrollment, compared to the percent who did not have a resume before the program. We will adjust our p-values for multiple hypothesis testing and report the adjusted p-values in the appendix of the final report.

For the implementation analysis, program fidelity will be descriptively reported by the percentage of enrolled participants who receive: 1) any primary workshops, 2) employment supports, 3) substantive service contacts, 4) referrals. The program aims to provide all participants each of these four program components, so the percentage of participants who receive each of these will be compared to the 100% benchmark. Number of substantive service contacts per participant will also be compared to the benchmark of 8 SSCs set by OFA for FIRE grantees.

Exploratory analysis will examine how dosage varies by workshop characteristics (e.g., timing and length of sessions) and participant characteristics (e.g., age, employment status, relationship status).

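### The attitude outcomes (R1, R4, R6) can be measured only in fathers who complete the program and attend the last session, but they share one unrestricted target population with the one-year outcomes, and loss between entrance and exit is never assessed

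*Protocol*

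**What the plan says.** **Who supplies each wave.** Protocol 9.3 places the post-test "during the last workshop session – approximately 4 weeks after enrollment". Protocol 9.4 adds that "only those individuals who complete the program and who are at the data collection session will participate" in this wave. The nFORM and OLLE post-surveys are taken in the same session, so the limit applies whichever instrument is used. For the later wave, Protocol 9.4 states: "All program participants, even those who do not complete the program, will be sent a 1-year follow-up survey", given consent and a baseline survey. Protocol 9.3 agrees: "Participants who did not complete the program will still be eligible for a follow-up survey as long as they consented".

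**How outcomes map to waves.** The SAP (Identify study sample) takes fathers who consented and "took both an entrance and exit survey (for attitudinal outcomes) or entrance and follow-up survey (for behavioral outcomes"). Its measure table draws all three attitude outcomes from entrance and exit, and all four behavior outcomes from entrance and one-year follow-up.

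**Population named.** Protocol 1.2 enters the same target population for R1 to R7: adult community fathers with children aged 24 or younger in high-poverty communities. Completion is not a condition. Protocol 8.1, asked how this population differs from those served by the grant, answers "No difference, all program participants will be study participants". The SAP (Analytic approach) describes both outcome families as change "among program participants before and after primary workshops".

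**Non-response.** The SAP (Assessing non-response bias) plans its comparison for each primary outcome. It lists three groups: no survey after the applicant survey, pre-survey only, and pre plus follow-up. Protocol 3 defines behaviors as primary and attitudes as secondary. Missing outcomes are not imputed.

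**The concern.** The two outcome families follow different rules after dropout. A father who stops early, or who finishes but misses the last session, cannot enter R1, R4 or R6. The same father can enter R2, R3, R5 and R7. The attitude sample is therefore selected on something that happens after enrollment, while its target population is written as if it were not.

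Two things are at stake. First, an attitude gain seen in completers may be read as the change in all fathers the program enrolled. Second, Protocol 3 ties attitudes and behaviors together in one logic model, so readers will set the two results side by side although they come from differently composed samples. Nothing planned would show them how different: the non-response check skips the exit pair, and the exploratory dosage analysis asks what predicts dosage, not how outcomes vary with it.

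**Working it through.** The documents give no completion rate, effect size or sample size for these outcomes, so there is no figure of the plan's own to reproduce. The check is mainly textual, with an illustration of scale.

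**Step 1: sample against stated population.**

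| | R1, R4, R6 | R2, R3, R5, R7 |
|---|---|---|
| Survey pair (SAP measure table) | entrance, exit | entrance, one-year follow-up |
| Who can supply the second survey (Protocol 9.3, 9.4) | completers present at the last session | consented fathers with a baseline survey, completers or not |
| Target population (Protocol 1.2) | all eligible community fathers | the same |
| Non-response comparison (SAP) | none | pre-only against pre plus follow-up |

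The second row differs between the columns and the third does not. The last row follows from reading the SAP's limit to primary outcomes together with Protocol 3. If the SAP meant the term loosely and included attitudes, the gap would remain: no listed group is defined by the exit survey, and a father with entrance and exit but no follow-up fits none of the three.

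**Step 2: possible size of the difference.** Let c be the share of fathers who complete and take the exit survey, d the mean change in them, and r the change in the others as a fraction of d.

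- All-participant change = c·d + (1 − c)·r·d
- Overstatement factor = d / all-participant change = 1 / [c + (1 − c)·r]

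The factor does not depend on d; d = 0.30 points is used only to show the scale. c, d and r are all assumptions.

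| c | r = 0: change, factor | r = 0.5: change, factor | r = 1: change, factor |
|---|---|---|---|
| 60% | 0.18, 1.67 | 0.24, 1.25 | 0.30, 1.00 |
| 70% | 0.21, 1.43 | 0.255, 1.18 | 0.30, 1.00 |
| 80% | 0.24, 1.25 | 0.27, 1.11 | 0.30, 1.00 |
| 90% | 0.27, 1.11 | 0.285, 1.05 | 0.30, 1.00 |

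Example, c = 60% and r = 0.5: 0.6 × 0.30 + 0.4 × 0.15 = 0.18 + 0.06 = 0.24, and 0.30 / 0.24 = 1.25. If the others changed more than completers (r above 1), the factor would fall below 1, so the direction is open too.

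**Step 3: how many fathers.** Protocol Program Summary plans 63 + 4 × 125 = 563 fathers in the primary workshop. This is a service target, not a study enrollment figure. Applied to 563, 90% completion gives 507 and leaves 563 − 507 = 56; 60% gives 338 and leaves 563 − 338 = 225. Those 56 to 225 fathers could not contribute to R1, R4 or R6. They could still be sent the one-year survey if they consented and took a baseline survey; how many would respond is unknown.

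**The case against.** The strongest reply is that this is a deliberate design: two kinds of question with two matching samples. Protocol 1.1 words R1, R4 and R6 as change once the program has been completed, and R2, R3, R5 and R7 as change one year from enrollment. The SAP openly defines a separate sample for each family, and its t-test sentence refers to the analytic sample for each outcome. This stands as disclosure. It does not settle the population: Protocol 1.2 still names one unrestricted group, and no text confines the attitude conclusions to completers.

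Several stronger readings are tempting, and the documents do not support them:

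- *That the plan says attitude results will be reported for all enrolled fathers.* No text says so; it is a risk left by the labeling. The answer in Protocol 8.1 responds to a template question about who the grant serves and does not describe an analytic sample.
- *That the phrase about primary workshops is false for every non-completer.* One year is after the workshops for anyone who attended some. The phrase fails only for fathers with no attendance, whose number is unknown.
- *That dropouts alone could produce an attitude gain with no behavior gain.* If 10% to 40% of one-year respondents were non-completers with no change, a gain of 0.30 in completers would appear as 0.30 × 0.9 = 0.27 down to 0.30 × 0.6 = 0.18, which is smaller but not zero. Nor is that a bias: it is the correct mean for the mixed sample. The families also differ in construct and in timing, about 4 weeks against one year.

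It can also be said that Protocol 1.2 labels all seven questions exploratory, although Protocol 3 calls the outcomes confirmatory. Protocol 5 treats each change as an upper limit on benefit because there is no counterfactual. That caveat concerns attribution, not who was measured. Finally, the SAP cites a CONSORT diagram in Appendix C, which is not in the text available for this review. It may already give some of the counts requested below. It would not change the stated population or the scope of the non-response comparison.

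**Conclusion.** The point holds as a mismatch between the attitude sample and its stated population, together with a gap in the non-response plan. R1, R4 and R6 can be estimated only in completers present at the last session; their target population does not say so, and entrance-to-exit loss is not assessed. This rests on the text alone.

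A reader might go further and infer that the attitude results are inflated. The documents cannot show that. The factors of 1.11 to 1.67 (no change in non-completers) and 1.05 to 1.25 (half the change) depend on an assumed 60% to 90% completion, and the factor is 1.00 if both groups change equally. Protocol 9.4 expects fairly modest attrition for the post-program collection but gives no rate. The correction is worth making before the final report, without any suggestion that the design has failed.

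**What to change.** 1. In Protocol 1.2 and SAP Analytic approach, restrict the population and conclusions for R1, R4 and R6 to *enrolled fathers who completed the core workshop and took the exit survey*. Beside each result, report the number and percent of consented, baseline-surveyed fathers this represents.
2. In SAP Assessing non-response bias, extend the comparison to the entrance-plus-exit pair for the attitude outcomes, using the same applicant-survey characteristics.
3. Keep the full entrance-plus-follow-up sample for R2, R3, R5 and R7. Add one descriptive table of the same changes (before-and-after percentages for the binary outcomes) for exit-survey takers against all others. Label it self-selected and collapse sparse groups.
4. In SAP Analytic approach, describe the behavioral outcomes as change *from enrollment to one year, regardless of completion* in place of the phrase about primary workshops.

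Cost: wording, one extended comparison and one extra table, all from nFORM and OLLE data the plan already collects. Post-test collection was scheduled to end on 7/1/2024 and the SAP is dated 1/16/2025, so on that schedule the exit sample can no longer be broadened; labeling and reporting are the remedies left. The downside is a narrower attitude conclusion and a subgroup table that supports no causal reading.

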10. IRB/PROTECTION OF HUMAN SUBJECTS

Please describe the process for protection of human subjects, and IRB review and approval of the proposed program and evaluation plans. Name the specific IRB to which you expect to apply.

Solutions IRB, a private commercial Association for the Accreditation of Human Research Protection Programs Inc. (AAHRPP) fully accredited Institutional Review Board, will ensure that this study is approved before any research activities take place. MER has had 14 research studies approved by Solutions IRB over the past four years, has completed over 15 annual check-in reports, and has submitted timely amendments when changes to studies needed to take effect.

All submissions are completed online, so turnaround for a new study approval is between 24 to 72 hours, though the full approval process can take approximately one to two weeks depending on the number of questions and requested revisions that the IRB makes. In the IRB application submission, we will include descriptions of project staff, locations of study sites, the funding source, incentives, summary of activities, participant population, recruitment plans, risks and benefits, confidentiality of data, and the informed consent process along with all materials to be used in the study such as participant forms and surveys.

This project will be submitted for IRB approval in early March 2021 to receive official approval to begin enrollment and data collection beginning in April 2021.

